Appendix H. PUBLICATION POLICY

All unpublished information given to the investigator by the sponsor shall not be published or disclosed to a third party without the prior written consent of the sponsor.

The results of this study may be published or presented at scientific meetings. If this is foreseen, the investigator agrees to submit all manuscripts or abstracts to the sponsor before submission. This allows the sponsor to protect proprietary information and to provide comments.

The sponsor will comply with the requirements for publication of study results: "Recommendations for the Conduct, Reporting, Editing, and Publication of Scholarly Work in Medical Journals" (International Committee of Medical Journal Editors [ICMJE] Recommendations 2017). Publication of the results will occur in a timely manner according to applicable regulations. In accordance with standard editorial and ethical practice, the sponsor will generally support publication of multicenter studies only in their entirety and not as individual investigational center data. In this case, a coordinating investigator will be designated by mutual agreement.

Authorship will be determined by mutual agreement and in line with ICMJE authorship requirements:

- substantial contributions to the conception or design of the work; or the acquisition, analysis, or interpretation of data for the work
- drafting the work or revising it critically for important intellectual content
- final approval of the version to be published
- agreement to be accountable for all aspects of the work in ensuring that questions related to the accuracy or integrity of any part of the work are appropriately investigated and resolved

The publications committee established by the sponsor will oversee this process. Additional publications may follow. Policies regarding the publication of the study results are defined in the financial agreement.

No patent applications based on the results of the study may be made by the investigator nor may assistance be given to any third party to make such an application without the written authorization of the sponsor.

LIST OF FIGURES

Figure 1: Operational Characteristics Calculated for the Study Design17

LIST OF ABBREVIATIONS AND DEFINITIONS OF TERMS

Abbreviation	Term
ACT	Asthma Control Test
App	smart device application
BIPQ	Brief Illness Perception Questionnaire
BMI	body mass index
BMQ	Beliefs about Medicines Questionnaire
CAE	clinical asthma exacerbation
CI	confidence interval
CRF	case report form
CSR	clinical study report
DHP	Digital Health Platform
DS	Digital System
DTP	direct-to-patient
ED	emergency department
ET	early termination
eMDPI	multidose dry powder inhaler with integrated electronic module
GERD	gastroesophageal reflux disease
GINA	Global Initiative for Asthma
HCP	healthcare professional
ICS	inhaled corticosteroid
iHCP	investigational center healthcare provider
IMP	investigational medicinal product
IRT	interactive response technology
ITT	intent-to-treat
LABA	long-acting beta ₂ agonist
LAMA	long-acting muscarinic antagonist
MAR	missing at random
MedDRA	Medical Dictionary for Regulatory Activities
MI	multiple imputation
Mini-AQLQ	Mini Asthma Quality of Life Questionnaire
mITT	modified intent-to-treat
PIF	peak inhalation flow
R&D	Research and Development
RTSM	Randomization and Trial Supply Management

Abbreviation	Term
SABA	short-acting beta ₂ agonist
SAP	statistical analysis plan
SD	standard deviation
SE	standard error
SoC	standard of care
SOC	system organ class
SOP	standard operating procedure
SUS	System Usability Scale
WHO	World Health Organization
WPAI	Work Productivity and Activity Impairment

INTRODUCTION

This Statistical Analysis Plan (SAP) describes the planned analysis and reporting for Teva Branded Pharmaceutical Products Research and Development (R&D) study FSS-AS-40139 (**CONN**ected Electronic Inhalers Asthma **CO**ntrol Trial 2 (“CONNECT 2”), a 24-Week Treatment, Multicenter, Open-Label, Randomized, Parallel Group Comparison, Feasibility Study of Standard of Care Treatment Versus the eMDPI Digital System, to Optimize Outcomes in Patients at Least 13 Years of Age or Older with Asthma), and was written in accordance with GSD_SOP_702 (SAP).

The reader of this SAP is encouraged to read the study protocol for details on the conduct of this study, the operational aspects of clinical assessments, and the timing for completing the participation of a patient in this study.

The SAP is intended to be in agreement with the protocol, especially with regards to the primary and all secondary endpoints and their respective analyses. However, the SAP may contain more details regarding these particular points of interest, or other types of analyses (e.g. other endpoints). When differences exist in descriptions or explanations provided in the study protocol and this SAP, the SAP prevails; the differences will be explained in the Clinical Study Report (CSR).

1. STUDY OBJECTIVES AND ENDPOINTS

1.1. Primary and Secondary Study Objectives and Endpoints

The primary and secondary study objectives and endpoints are:

Objectives	Endpoints
The primary objective of this study is to demonstrate the effectiveness of the Digital System (DS) compared to a Standard of Care (SoC) group.	The primary endpoint is the proportion of patients for the DS and SoC groups achieving meaningful improvement, which is defined as an Asthma Control Test (ACT) score greater than or equal to 20, or a clinically important improvement in asthma control as defined by an increase of at least 3 ACT units from baseline at the end of the 24-week treatment period.
The secondary objective (#1) is to describe the asthma management actions by investigational center healthcare providers (iHCPs) for all patients in both groups.	
This secondary endpoint will describe the frequency and types of interventions done to improve asthma control including:
 
 • number of discussions regarding inhaler technique or adherence • number of adjustments of therapy including: 
 ○ increased or decreased doses of inhaled medication ○ change to different inhaled medication ○ additional inhaled medication ○ addition of a systemic corticosteroid medication for asthma or another controller, including a long-acting muscarinic antagonist (LAMA) or biologics • frequency of intervention to manage comorbid conditions associated with poor asthma control (gastroesophageal reflux disease [GERD], sinusitis, etc.)
The secondary objective (#2) is to evaluate short-acting beta ₂ agonist (SABA) usage and the number of SABA-free days in the DS group.	This secondary endpoint is the change from baseline in the mean weekly SABA usage and the change from baseline in the number of SABA-free days over the 24-week treatment period for the DS group.

Objectives	Endpoints
The secondary objective (#3) is to evaluate adherence patterns to maintenance treatment (FS eMDPI) in the DS group.	This secondary endpoint is the change from baseline in adherence to maintenance treatment (FS eMDPI), defined as the proportion of actual inhalation doses prescribed over the 24-week treatment period.
The secondary objective (#4) is to assess behavioral correlates of responsiveness to digital health technology among patients for all patients in both groups.	This secondary endpoint is the assessment of patients' beliefs and perceptions about their disease and treatment, utilizing the Beliefs about Medicines Questionnaire (BMQ) and the Brief Illness Perception Questionnaire (BIPQ) to both the DS and SoC groups, patients 18 years of age or older, describing their behavioral profile at baseline and at the end of the study.
The secondary objective (#5) is to evaluate work productivity and activity impairment in asthma patients in both groups.	This secondary endpoint is the change from baseline measured by the Work Productivity and Activity Impairment (WPAI) questionnaire, completed by patients 18 years of age or older in both groups, at baseline and at the end of the 24-week treatment period.
The secondary objective (#6) is to assess the usability and acceptability of the DS by patients in the DS group and the investigational center personnel.	This secondary endpoint is the assessment of the DS (eMDPI, smart device application [App], and dashboard) acceptability and usability, utilizing the System Usability Scale (SUS), completed by the patients in the DS group, 18 years of age or older, and the investigational center personnel at the end of the study.
The secondary objective (#7) is to evaluate the safety of FS eMDPI and Albuterol eMDPI.	This secondary endpoint is the reporting of adverse events related to FS eMDPI and Albuterol eMDPI at participating investigational centers. The safety endpoints for this study include the following for all patients in both groups: 
 • adverse event data • adverse device effect data

Notes: The Digital System (DS) group will include eligible study population patients who will use the DS (FS eMDPI, Albuterol eMDPI, and common App, Digital Health Platform [DHP; Cloud solution], and dashboard) during the treatment period. The Standard of Care (SoC) group will include eligible patients who will be treated with their current treatment provided by the investigational center to the patient, based on asthma guidelines.

1.2.

[REDACTED]

[REDACTED]

[REDACTED]

[REDACTED]

[REDACTED]

[REDACTED]

2. STUDY DESIGN

2.1. General Design

This is a 24-week treatment, multicenter, open-label, randomized, parallel group comparison feasibility study of SoC treatment versus using the eMDPI DS, including inhaler, App, Digital Health Platform (DHP; cloud solution), and dashboard, to optimize outcomes in patients at least 13 years of age or older with asthma.

The study will consist of a screening/baseline visit (Visit 1), a 24-week open-label treatment period with Visit 2 (either in-person or remote) at Week 12 and Visit 3 at Week 24, and a follow-up telephone call (2 weeks following treatment completion).

Patients with suboptimal asthma control will be enrolled in the study and randomized, in a 4:3 ratio, respectively, to 1 of 2 parallel groups ([Table 1](#)), stratified by investigational center.

Table 1: Description of Treatment Groups

DS group	SoC group
FS eMDPI ^a + App	Current ICS/LABA and any additional controller medication for asthma (except for biologics)
Albuterol eMDPI + App	Current rescue medication
DHP (Cloud solution)	Not applicable
Provider-facing dashboard	Not applicable

^a iHCP can add another controller medication other than an ICS with LABA, including a biologic, to the DS patient's treatment, if needed.

Albuterol eMDPI=Albuterol electronic multidose dry powder inhaler; App=smart device application; DHP=Digital Health Platform; DS=Digital System; FS eMDPI=fluticasone propionate/salmeterol electronic multidose dry powder inhaler; ICS=inhaled corticosteroid; iHCP=investigational center health care provider; LABA=long-acting beta₂ agonist.

The Digital System (DS) group patients will use the FS eMDPI and the Albuterol eMDPI with a common App, DHP (Cloud solution), and dashboard. The SoC group patients, who will include eligible patients treated with their current treatment provided by the investigational center to the patient, based on asthma guidelines, will not use the DS during the treatment period. Similar data will be collected regarding outcomes for both groups: ACT after 24 weeks, BMQ, BIPQ, Mini-AQLQ, and WPAI questionnaire responses, and the frequency of CAEs.

All patients will have a screening/baseline visit (Visit 1), at which they will be asked if they own a smart device and use different applications on their smartphones. A baseline ACT score for all patients, and BMQ, BIPQ, Mini-AQLQ, and WPAI questionnaire responses for patients 18 years of age or older will be collected. At Visit 1, patients in the DS group will be trained on the use of the eMDPI (including instructions on how to use both the eMDPIs and the App). Upon demonstrating competency, patients in the DS group will have their maintenance inhaled corticosteroid (ICS) with long-acting beta₂ agonist (LABA) switched to the FS eMDPI (at a dose of fluticasone comparable to their most recent current ICS dose) and their rescue treatment switched to the Albuterol eMDPI. All other asthma maintenance medications, except for ICS with LABA, may be continued. The iHCP can add another controller medication other than an

ICS with LABA, including a biologic, to the DS patient's treatment, if needed. Patients in the SoC group will be reimbursed or given a voucher to use to purchase their existing maintenance ICS with LABA and rescue medications. Patients in the DS group will receive a new FS eMDPI device and a new Albuterol eMDPI device at Visit 1 and 1 FS eMDPI device and 1 Albuterol eMDPI device at Visit 2. Periodically after Visits 1 and 2, patients will be shipped a new FS eMDPI device, which they will need to pair with the App. The patient will immediately stop using the old device and switch to the new device. Extra Albuterol eMDPI devices may be shipped as needed, based on the clinical judgment of the investigator. Upon receipt, the patient will pair the new device with the App and will immediately stop using the old device and switch to the new device. To trigger direct-to-patient (DTP) shipments, after Visit 1, the investigational center will receive periodic email reminders to access the interactive response technology (IRT) system to confirm the dose of test investigational medicinal product (IMP) to be shipped to the patient. Confirmation of the dose is required before the next shipment can be sent.

Investigational centers will receive similar instruction regarding features of the App, as well as features of the associated dashboard, which mirrors the digital information obtained from the eMDPIs and App, including frequency and times of SABA rescue use and associated inspiratory flow parameters measured by the eMDPI with each inhalation.

The SoC group will be followed according to the clinical judgment of the investigator; the asthma of patients in the SoC group will be managed in a manner consistent with the clinical judgement of the investigator and based on asthma management guidelines (eg, Global Initiative for Asthma [GINA]). Similar to the management of the SoC group, the DS group patients will be followed by the investigational centers with the addition of objective information on FS eMDPI and Albuterol eMDPI usage being available to both patients and investigational centers through the App and the dashboard, respectively. The iHCPs will check the dashboard at least once a week and use this information, along with any other additional information about the patient, as per their clinical judgement, to modify patients' asthma management. The investigator may, if indicated, modify the patient's regime, including adding asthma controllers or biologics as otherwise clinically indicated in the judgement of the investigator. Clinically Driven Assessments for both groups, if necessary, should be arranged, per the clinical judgement of the iHCP managing the patient, and can be via a telephone call or an on-site visit.

For all patients, at Visit 2, Visit 3, and any Clinically Driven Assessments, if necessary, the iHCP will record answers to Asthma Management questions, including discussions regarding adherence, or inhaler technique, treatment adjustments, or additions of new treatments, including biologic medication usage. Additionally, in the case of a Clinically Driven Assessment (for patients in the DS group), the iHCP will be asked whether or not the contact with the patient was originated from the iHCP interaction with the dashboard.

Visit 2 (if it is an in-person visit) will include dispensing of new inhalers to the DS group patients and return of used or unused inhalers that were dispensed to the patients previously. New FS eMDPI devices will continue to be shipped directly to patients periodically after Visit 2 until the end of treatment. The ACT will be completed and scores registered.

At the end of the treatment period (24 weeks), final assessments of the DS and SoC groups will be completed, as specified in Table 5 of the study protocol, and the rest of the inhalers that were dispensed to the DS group patients will be returned. A follow-up telephone call will be made by

the investigational center to all patients, 2 weeks later, and will confirm that the DS group patients have returned to their previous asthma treatments.

It should also be noted that no specific clinical decisions are being mandated. One secondary objective of this study is to describe how clinicians actually use the information provided by the DS to manage their patients.

Study procedures and assessments with their timing are summarized in Table 5 of the study protocol.

2.2. Randomization and Blinding

This is an open-label study and patients will be randomly assigned to the DS group or SoC group in a 4:3 ratio stratified by investigational center, using a Randomization and Trial Supply Management (RTSM) system. Since this is an open-label study, blinding is not applicable.

2.3. Data Monitoring Committee

There will be no Data Monitoring Committee for this study.

[figure not shown]
2.4. Sample Size and Power Considerations

The sample size was selected based on a Bayesian approach which allows for a range of underlying proportions rather than a fixed predefined value.

A total of 388 patients will be enrolled in the study (accounting for 10% early dropouts), 200 patients in the DS group and 150 patients in the SoC group, to be available for analysis. The sample size determination was made assuming binomial distribution for the primary endpoint. An informative prior for the SoC group (Beta [9.52, 11.88]) was selected to reflect the belief that the response rate of the SoC group is between 30% and 60% (most likely 45%, [Merchant 2016](#)) and the effect size between groups of 13% difference in response rates was considered clinically meaningful.

In addition, an informative prior for the SoC group was selected to ensure that the mean square error for the Bayes estimate from the informative prior is superior to the maximum likelihood estimate over a range of 30% and 60% of anticipated proportion for SoC group.

It should be noted that both power and Type 1 error are dependent on the absolute difference between the DS and the SoC groups as illustrated in [Figure 1](#) below by the operational characteristics calculated for the study design.

Figure 1: Operational Characteristics Calculated for the Study Design

MSE=maximum likelihood estimation; MSE=mean squared error

A non-informative prior (Beta [0.5,0.5]) for the DS group was selected due to lack of availability of data in the DS group.

With assumptions of response rates of 58% and 45% for the DS and SoC groups, respectively, sample size and randomization ratio, the probability of the posterior odds ratio (OR) of improvement (ie, $OR > 1$) for the DS group versus the SoC group of at least 0.95 is about 82%. This will ensure a 1-sided 5% Type 1 error rate and 78% power for an effect size for 13% difference between the groups provided that the proportion of responders in the SoC group is 45%.

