9.1. Sample Size and Power Considerations

The sample size was selected based on a Bayesian approach which allows for a range of underlying proportions rather than a fixed predefined value.

A total of 388 patients will be enrolled in the study (accounting for 10% early dropouts), 200 patients in the DS group and 150 patients in the SoC group, to be available for analysis. The sample size determination was made assuming binomial distribution for the primary endpoint. An informative prior for the SoC group (Beta [9.52, 11.88]) was selected to reflect the belief that the response rate of the SoC group is between 30% and 60% (most likely 45%, Merchant 2016) and the effect size between groups of 13% difference in response rates was considered clinically meaningful.

In addition, an informative prior for the SoC group was selected to ensure that the mean square error for the Bayes estimate from the informative prior is superior to the maximum likelihood estimate over a range of 30% and 60% of anticipated proportion for SoC group.

It should be noted that both power and Type 1 error are dependent on the absolute difference between the DS and the SoC groups as illustrated in Figure 5 below by the operational characteristics calculated for the study design.

[figure not shown]

Figure 5: Operational Characteristics Calculated for the Study Design

MLE=maximum likelihood estimation; MSE=mean squared error

A non-informative prior (Beta [0.5,0.5]) for the DS group was selected due to lack of availability of data in the DS group.

With assumptions of response rates of 58% and 45% for the DS and SoC groups, respectively, sample size and randomization ratio, the probability of the posterior odds ratio (OR) of

CLN0035849 Version 2.0 Approved

Page 68 of 98

improvement (ie, OR>1) for the DS group versus the SoC group of at least 0.95 is about 82%. This will ensure a 1-sided 5% Type 1 error rate and 78% power for an effect size for 13% difference between the groups provided that the proportion of responders in the SoC group is 45%.

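### The sample-size section gives one decision rule two powers (82% and 78%) for the same scenario, and does not say that its Type 1 error depends on the true SoC response rate

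*SAP*

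**What the plan says.** SAP section 2.4 describes a Bayesian sample-size calculation, and Protocol section 9.1 and the synopsis carry the same text. It plans for "200 patients in the DS group and 150 patients in the SoC group, to be available for analysis". "An informative prior for the SoC group (Beta [9.52, 11.88]) was selected to reflect the belief" that the SoC response rate lies between 30% and 60%, most likely 45%. The DS arm has a Beta(0.5, 0.5) prior. The success criterion is a posterior probability of at least 0.95 that the odds ratio exceeds 1.

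"With assumptions of response rates of 58% and 45% for the DS and SoC groups, respectively", the section first gives the probability of meeting that criterion: "for the DS group versus the SoC group of at least 0.95 is about 82" percent. The next sentence then says "This will ensure a 1-sided 5% Type 1 error rate and 78% power for an effect size for 13% difference", and ends by making these figures conditional on a SoC responder proportion of 45%. Protocol section 9.1 agrees: "This will ensure a 1-sided 5% Type 1 error rate and 78% power".

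The section also warns that the operating characteristics vary. It says "both power and Type 1 error are dependent on the absolute difference" between the groups and refers to a figure, which is not reproduced in the copy reviewed.

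**The concern.** The probability of meeting the success criterion when the rates are 58% and 45% is the power of that criterion. The text gives it as 82%, then as 78%, for the same rates, sample sizes and SoC assumption. The opening words of the second sentence tie the 78% and the 5% to the rule just described, so a reader has no reason to think that two different rules are meant.

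The second issue is what drives the Type 1 error. Under the null hypothesis the difference between the groups is zero, so Type 1 error cannot vary with that difference. With an informative prior on one arm only, it varies with the true SoC rate, because the prior pulls the SoC estimate towards about 45% and leaves the DS estimate almost untouched. The section says the Bayesian approach was chosen to allow for a range of underlying proportions, yet the readable text gives a Type 1 error at one point only. A reader could take 5% as the false-positive rate across the range.

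**Working it through.** **Inputs** (SAP section 2.4): 200 DS and 150 SoC patients; DS prior Beta(0.5, 0.5); SoC prior Beta(9.52, 11.88); success if P(OR > 1 | data) ≥ 0.95; planning rates 58% and 45%; SoC range 30% to 60%. The sample sizes agree with the 4:3 allocation in SAP section 2.2.

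**Step 1: the 82%.** With x responders of 200 on DS and y of 150 on SoC, the posteriors are Beta(0.5 + x, 200.5 − x) and Beta(9.52 + y, 161.88 − y). Success is P(p_DS > p_SoC | x, y) ≥ 0.95, which is the same event as OR > 1. Summing Bin(x; 200, p_DS) × Bin(y; 150, p_SoC) over the successful pairs among all 201 × 151 outcomes gives:

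- p_DS = 0.58, p_SoC = 0.45: power 0.817, the plan's figure of about 82%
- p_DS = p_SoC = 0.45: Type 1 error 0.046

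**Step 2: the 78% and 5%.** A one-sided 5% pooled z-test on the same sample sizes:

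- pooled rate = (200 × 0.58 + 150 × 0.45) / 350 = 183.5 / 350 = 0.5243
- SE under the null = √[0.5243 × 0.4757 × (1/200 + 1/150)] = 0.0539
- SE under the alternative = √[0.58 × 0.42/200 + 0.45 × 0.55/150] = 0.0536
- power = Φ[(0.13 − 1.645 × 0.0539) / 0.0536] = Φ(0.77) = 0.780

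Repeating the step 1 enumeration with Beta(0.5, 0.5) in both arms gives power 0.779 and Type 1 error 0.0499 at 45%. So 82% reproduces with the SoC prior, and 78%/5% reproduces without it.

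**Step 3: the section 2.4 rule across the sponsor's SoC range.**

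| True SoC rate | Type 1 error, section 2.4 rule | Type 1 error, Beta(0.5, 0.5) both arms | Power for +13 points, section 2.4 rule |
|---|---|---|---|
| 30% | 1.9% | 5.1% | 73.6% |
| 40% | 3.6% | 5.0% | 78.4% |
| 45% | 4.6% | 5.0% | 81.7% |
| 50% | 5.9% | 5.0% | 85.2% |
| 55% | 7.4% | 5.0% | 88.9% |
| 60% | 9.3% | 5.0% | 92.5% |

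Type 1 error passes 5% at a SoC rate of about 46.6%. The prior Beta(9.52, 11.88) has about 42% of its weight above that point and about 7% above 60%. Averaged over the prior, with DS equal to SoC, Type 1 error is about 5.0%.

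**Step 4: why it rises.** The SoC prior counts as 9.52 + 11.88 = 21.4 patients with mean 9.52 / 21.4 = 0.445. If 90 of 150 SoC patients respond (60%), the posterior mean is (9.52 + 90) / (21.4 + 150) = 0.581, about 2 points too low, which favours DS. If 45 of 150 respond (30%), it is 54.52 / 171.4 = 0.318, about 2 points too high, which works against DS.

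**Step 5: how far this carries over to the primary model.** SAP section 6.2.2 uses normal priors on the logit scale, baseline ACT and a random center effect. A simulation of those priors without ACT and center (Laplace approximation, 6,000 trials per scenario) gave power 82% and Type 1 error 4.2% at SoC 45% and 9.5% at 60%, close to step 3. Adding uncentered baseline ACT, as coded in the SAP, changes this. The documents give no ACT distribution or slope. Assuming ACT roughly normal with mean 14 and SD 3, limited to 5–18, and a log-odds slope of 0 to −0.1 per unit, Type 1 error was about 5–10% at SoC 45% and 7–12% at 60%.

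**The case against.** The sentence that gives 5% and 78% carries its own condition, a SoC rate of 45%. There the section 2.4 rule has 4.6% Type 1 error and 81.7% power, so 5% holds as an upper bound and 78% is cautious. The 9.3% and 73.6% arise at 60% and 30%, where the sentence claims nothing. This stands. A reader might infer that the documents promise 5% throughout 30% to 60% and break that promise, but the text does not support that reading.

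The documents also warn that the operating characteristics vary, and the figure may plot Type 1 error against the SoC rate. That possibility must be allowed for. It would not reconcile 82% with 78%, and the accompanying text would still name the wrong driver of Type 1 error.

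A Type 1 error that depends on the control rate is an ordinary result of an informative control prior, and here it averages about 5.0% over that prior. That is fair, and a reason to report the dependence rather than to call the design faulty.

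SAP section 7 says there is no hypothesis testing, and section 6.2.2 states no 0.95 threshold. But section 2.4 itself claims a Type 1 error and a power, and section 6.2.2 sets out null and alternative hypotheses for the treatment coefficient.

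Finally, sensitivity analysis 1 (SAP section 6.2.3) fits a model without priors, so dependence on the prior would be partly visible. It also changes the missing-data handling and drops center. Sensitivity analysis 2 keeps the same priors. Neither isolates the effect of the SoC prior.

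**Conclusion.** The point holds in a limited form. For 58% against 45%, the section 2.4 rule has about 82% power; the 78% attributed to it is 3.7 points lower than the enumerated 81.7%. Its Type 1 error is 4.6% at SoC 45%, within the stated 5%, but ranges from 1.9% to 9.3% over the SoC rates the sponsor considers plausible and exceeds 5% above about 46.6%. The text attributes the variation in Type 1 error to the difference between groups when it comes from the SoC rate.

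Two further inferences go beyond the documents. A reader might conclude that 78%/5% was in fact computed for a test without the SoC prior. The numerical match is close, but the documents do not state the method, and the inconsistency does not depend on its source. A reader might also take 9.3% as the false-positive rate of the final analysis. It belongs to the two-arm beta-binomial rule of section 2.4, with exactly 200 and 150 analysed patients and a 0.95 threshold; the section 6.2.2 model differs.

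This should be corrected, but it does not invalidate the design or change the sample size.

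**What to change.** In SAP section 2.4, Protocol section 9.1 and the synopsis:

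- Give one power for the section 2.4 rule: 82%, with Type 1 error 4.6%, at SoC 45%.
- Either name the method behind 78%/5% or delete that pair.
- State that Type 1 error depends on the true SoC rate and give its range over 30% to 60% (1.9% to 9.3%), labelled as applying to the two-arm beta-binomial rule.

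In SAP section 6.2.2, state the 0.95 threshold if it is the success criterion, and confirm the operating characteristics by simulation for that model, including baseline ACT and center as coded.

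In SAP section 6.2.3, add one run of the section 6.2.2 model with a non-informative prior in place of the informative prior on β0, with everything else unchanged. The vague normal prior already used for β2 (mean 0, variance 1000) would serve. This shows whether a positive result depends on the SoC prior.

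The cost is a wording change in three places, a simulation and one extra model run. The stated Type 1 error will look less favourable at SoC rates above the planning value. No extra patients are needed.
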